## 1. PROTOCOL SUMMARY

Title	Clinical Outcomes After Treatment with Restrata™ Wound Matrix in Diabetic Foot Ulcers (DFU) A Case Series of Initial Effectiveness and Safety Measures
Protocol Number	17-RES-001; Revision: 01
Protocol Approval Date	10/12/17
Indications for Use	Restrata™ Wound Matrix is intended for use in the management of wounds, including: Partial and full thickness wounds, pressure sores/ ulcers, venous ulcers, diabetic ulcers, chronic vascular ulcers, tunneled / undermined wounds, surgical wound (e.g., donor site/ grafts, post-laser surgery, post-Mohs surgery, podiatric wounds, wound dehiscence), trauma wounds (e.g., abrasions, lacerations, partial thickness burns, skin tears), and draining wounds.
Acera Device	Restrata™ Wound Matrix
Study Purpose	Inform design of randomized controlled trial of Restrata™ Advanced Wound Matrix
Enrollment Size	Minimum of 30 patients
Study Design	Prospective, single armed, non-randomized study with direct assignment
Assessment Intervals	Baseline and weekly for up to 12 weeks with a closure confirmation visit within 2 weeks after complete closure has been first determined
Endpoint	12 weeks with closure confirmation visit 2 weeks thereafter

## 2. INTRODUCTION & PURPOSE

### 2.1. Background and Purpose

The process of wound healing requires a coordinated effort of cellular recruitment and tissue growth. Regenerative matrix materials have been used to promote this coordination and provide immediate wound coverage to minimize the risks associated with infection and fluid loss. An ideal material for these purposes would serve as a healing scaffold, limit infection risk, minimize inflammation, be readily available for use, and be conformable to diverse wound surfaces. [1,2]

Human autografts and allografts, animal-based xenografts, and fully synthetic materials have been used clinically with varying degrees of success. Autograft availability is limited by definition, and creates iatrogenic morbidity at donor sites. Allografts and xenografts eliminate the morbidity associated with autografts, but introduce additional risks of inflammatory response and disease transmission. Furthermore, host rejection of allografts and xenografts remains a concern in wound populations where the rate of immune disease has been reported as high as 23%. [3]

To support the infiltration of fibroblasts, the deposition of new collagen, and re-epithelialization of the wound surface, the wound matrix material should persist in the wound for at least three weeks. [4] The timing of wound matrix degradation is therefore critical, as the wound matrix should resist degradation until sufficient new tissue growth has occurred. The susceptibility of biologic wound matrix materials to enzymatic degradation leads to a resorption rate that is poorly controlled, risking the premature degradation of the wound matrix prior to sufficient wound healing. [5]

There remains a need for materials that minimize inflammation and promote complete wound healing. [6,7,8] Electrospun fibrous scaffolds may meet this need by mimicking the structure of native extracellular environment while enabling resident cells to perform their roles in the healing cascade. [9,10] The purpose of the following study is evaluate the initial safety and effectiveness of Restrata™ Wound Matrix in treating diabetic foot ulcers in human subjects, and to inform the design of a randomized controlled trial of Restrata™ Wound Matrix

## **2.2. Intended Use/Indications**

The Restrata™ Wound Matrix is a sterile, single use device intended for use in local management of wounds. The Restrata™ Wound Matrix is a soft, white,

conformable, non-friable, absorbable matrix that acts as a protective covering for wound defects, providing a moist environment for the body's natural healing process to occur. Restrata™ is made from synthetic biocompatible materials and was designed to include a fibrous structure with high porosity, similar to native extracellular matrix. Restrata™ is a porous matrix with a defined rate of resorption that provides a scaffold for cellular infiltration and vascularization before completely degrading via hydrolysis. The device permits the ingress of cells and soft tissue formation in the defect space / wound bed. The device does not contain any human or animal materials or tissues.

Restrata™ Wound Matrix is supplied terminally sterile, in a single use double peel package in a variety of sizes. Restrata™ Wound Matrix may be fenestrated or meshed with a scalpel prior to application. Restrata™ must be fenestrated prior to use in any wound prone to exudate in order to permit effective exudate management. Contents of the package are guaranteed sterile and non-pyrogenic unless the package has been opened or damaged.

Restrata™ Wound Matrix is intended for use in the management of wounds, including: Partial and full thickness wounds, pressure sores/ ulcers, venous ulcers, diabetic ulcers, chronic vascular ulcers, tunneled / undermined wounds, surgical wound (e.g., donor site/ grafts, post-laser surgery, post-Mohs surgery, podiatric wounds, wound dehiscence), trauma wounds (e.g., abrasions, lacerations, partial thickness burns, skin tears), and draining wounds.

The benefits and risks of participation in this study will be described in the informed consent form.

### **3. STUDY DESIGN**

**Condition:** Diabetic Foot Ulcers (DFU)

**Aim:** Inform design of randomized controlled trial of Restrata™ Wound Matrix

**Number of Patients:** 30

**Number of Sites:** Up to 8

**Study Type:** Interventional

**Study Design:** Allocation: Non-randomized  
Endpoint Classification: Efficacy  
Intervention Model: Direct assignment  
Masking: Single Blind (Subject)  
Primary Purpose: Treatment

**Control Group:** None (Utilize historical / published data on outcomes using standard of care)

**Test Group:** Treatment of DFUs with Restrata™ Wound Matrix

### **Primary Outcome Measures:**

- Percent Wounds Closed [ Time Frame: Baseline and weekly for up to 12 weeks ]  
Wound healing will be assessed every week for 12 weeks or until the wound is completely closed, whichever occurs first. Persistence of wound closure will be verified via confirmatory visit within 2 weeks after complete closure has been first determined.

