### **Secondary Outcome Measures:**

- Decrease in Wound Area From Baseline [ Time Frame: Baseline and weekly for up to 12 weeks ]  
Wound area measurements will be made via tracing acetate every week for 12 weeks or until the wound is completely closed, whichever occurs first. Wound area will be verified via confirmatory visit within 2 weeks after complete closure has been first determined.
- Time to Wound Closure [ Time Frame: Baseline through 12 weeks ]  
The number of weeks until complete closure is first identified will be determined for each patient who has been deemed completely closed within the 12 week treatment period.

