### **5.4. Follow-Up Procedures (Weekly up to 12 weeks or until complete closure is first identified with a confirmation visit within 2 weeks thereafter; window for all visits is $\pm$ 3 days)**

At each of the interim timepoints subjects will return to the clinic for analysis / assessment of the following as indicated in the Schedule of Events in Appendix A:

- Measurement of wound area via acetate tracing
- Documentation of wound appearance via photograph
- Documentation of wound closure (if present)
- Gross observation of wound for evidence of infection

- Assessment of Quality of Life- Odor (only at 4, 8, 12 weeks  $\pm$  3 days)
- Assessment of Quality of Life- Itch (only at 4, 8, 12 weeks  $\pm$  3 days)
- Assessment of Quality of Life- Visual appearance
- Codes used to submit for reimbursement and amount (if any) reimbursed

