# 8. DATA ANALYSIS

## 8.1. Demographics and Outcomes

Descriptive statistics will be used to compare amongst experimental groups, along with confidence intervals where appropriate to measure effect size. Rates of adverse events will be tabulated by type, severity and device / procedure relatedness. Furthermore, statistics on the wound measurements over time and at the 12 week endpoint will be used to inform future study hypotheses.

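### No rule returns a wound found open at the confirmation visit to weekly assessment, so for first closures up to about Week 9 the later course and any re-closure by Week 12 go uncollected

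*Combined protocol and SAP*

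**What the plan says.** The rule appears in several places in the protocol.

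- **Section 3, Primary Outcome Measures.** "Wound healing will be assessed every week for 12 weeks or until the wound is completely closed, whichever occurs first". The next sentence adds the check: "Persistence of wound closure will be verified via confirmatory visit within 2 weeks after complete closure has been first determined".
- **Section 3, Secondary Outcome Measures.** Area follows the same rule: "Wound area measurements will be made via tracing acetate every week for 12 weeks or until the wound is completely closed, whichever occurs first". Time to closure is defined by first closure: "The number of weeks until complete closure is first identified will be determined for each patient", restricted to patients deemed closed within the treatment period.
- **Section 5.4 heading.** Weekly visits run to Week 12 or "until complete closure is first identified with a confirmation visit within 2 weeks thereafter", with a window of ±3 days on all visits.
- **Section 1.** The assessment row reads "Baseline and weekly for up to 12 weeks with a closure confirmation visit within 2 weeks after complete closure has been first determined". The endpoint row reads "12 weeks with closure confirmation visit 2 weeks thereafter", which ties the confirmation visit to Week 12 and not to the date of first closure.
- **Section 5.6.** This is the only text on wounds not confirmed closed. It covers patients who withdraw, by telephone or mail, and limits what is learned to the tertiary endpoints.
- **Section 8.1.** The analysis includes "statistics on the wound measurements over time and at the 12 week endpoint".
- **Appendix A.** There are weekly columns and a closure confirmation visit, with no branch for a wound found open at that visit.

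**The concern.** The confirmation visit exists because a wound that looks closed may not stay closed. The plan therefore expects some failed confirmations but gives no path for them. Take a wound first closed at Week 4 and found open at Week 6. As the schedule is written, it has no assessment for Weeks 7 to 12, which is six weekly visits. Those visits are missing because of the outcome, and no analysis can restore data that were not collected.

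Three results are affected:

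- Percent Wounds Closed has no stated count for such a wound. Counting it as closed credits a closure that failed. Counting it as not closed is wrong if it re-closed by Week 12, and nobody will know.
- The area series stops for these wounds, and the 12-week area is absent.
- Time to closure takes the date of first closure, so a failed closure can enter as a short healing time.

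The stated aim is to inform a randomised trial, and results will be set against historical or published data. Both uses need to know what kind of closure the percentage counts, and the trial's planners will want to know how often reopened wounds close again.

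**Working it through.** The plan gives no figure to reproduce: Section 8.1 is descriptive, and no power calculation or reopening rate is stated. The check is of the visit calendar, then of how much one wound weighs.

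**Calendar.** Inputs: weekly visits, confirmation within 2 weeks of first closure, window ±3 days (Sections 3 and 5.4). Week *k* is day 7*k*. Week 12 is day 84, with a window of days 81 to 87. The latest nominal confirmation is day 7*k* + 14. Using both windows late (first-closure visit +3, confirmation visit +3) gives 7*k* + 20.

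| First closure | Latest nominal confirmation | Both windows used late | Reaches Week 12? |
|---|---|---|---|
| Week 1 | 7 + 14 = day 21 | day 27 | No |
| Week 8 | 56 + 14 = day 70 | day 76 | No; the window opens on day 81 |
| Week 9 | 63 + 14 = day 77 | day 83 | Only with both windows used late |
| Week 10 | 70 + 14 = day 84 | day 90 | Yes, if done on the last nominal day |
| Week 11 | 77 + 14 = day 91 | day 97 | Can fall on either side of day 84 |
| Week 12 | 84 + 14 = day 98 | day 104 | Week 12 status is seen directly; confirmation follows |

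Weeks 2 to 7 behave as Weeks 1 and 8 do. So for first closures in Weeks 1 to 8, and nominally in Week 9, a wound found open has no scheduled visit at Week 12. For Weeks 10 to 12 it can have one.

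**Weight of one wound.** With 30 patients (Sections 1 and 3; 30 is the minimum), 1/30 = 3.3 percentage points.

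**Illustration.** Assumptions, neither in the documents: 15 of 30 wounds first close by Week 12, and 10 to 20% of these are open at the confirmation visit.

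- 15 × 0.10 = 1.5 wounds; 1.5/30 = 5 points.
- 15 × 0.20 = 3 wounds; 3/30 = 10 points.

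With 3 reopened, and exact (Clopper-Pearson) 95% intervals:

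- all first closures counted: 15/30 = 50.0% (31.3 to 68.7);
- the three not counted: 12/30 = 40.0% (22.7 to 59.4).

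The gap depends only on the number reopened. For 12 to 21 first closures and 1 to 3 reopenings it runs from 1/30 = 3.3 to 3/30 = 10 points.

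**The case against.** **The protocol does not forbid further visits.** A reader might infer that a reopened wound is barred from further assessment. The text does not say that; it is silent. Section 5.6 even suggests that a patient whose closure is unconfirmed is still in follow-up until 12 weeks, since leaving before then counts as withdrawal. This stands as a limit on the claim. It does not close the gap: Section 5.6 schedules nothing for a patient who has not withdrawn, and Section 5.4 ties the end of weekly visits to first closure. With up to 8 sites, silence also allows different practice at different sites.

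**Week 12 status is not lost for every such wound.** A reader might infer that it is never seen. The calendar shows otherwise for first closures at Weeks 10 to 12.

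**Reopening is recorded.** A reader might infer that the reopening rate is lost. The confirmation visit observes reopening up to that visit, and the area then. What is missing is the course afterwards and the time to re-closure.

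**The primary outcome may be closure by Week 12, not status at Week 12.** This is a natural reading of the time frame. On it, counting only confirmed closures settles the first closure, and a wound confirmed closed early needs no Week 12 visit. The remaining uncertainty is then limited to reopened wounds that close again in time. This reduces the size of the problem but does not remove it, and the plan does not state the confirmed-closure rule.

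**The study is small and descriptive.** True: no test is at risk. The effect is on an estimated proportion, its interval, the area series and the closure times.

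**Conclusion.** The point holds in this limited form. Followed as written, the schedule ends weekly assessment and tracing at first closure, and no provision brings back a wound found open at the confirmation visit. For first closures up to about Week 9, re-closure by Week 12 and the area at Week 12 then go uncollected. Separately, the time-to-closure definition can credit a closure that failed confirmation.

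The range of 5 to 10 points is an upper bound on assumed inputs, not an expected bias. It counts all 15 assumed closures, including those at Weeks 10 to 12 whose Week 12 status can be seen. If only confirmed closures count, only reopened wounds that re-close in time move the estimate. The change is worth making because the data cannot be recovered later and few patients would be affected.

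**What to change.** Keep the current schedule and make these changes.

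1. In Sections 3 and 5.4, state that a wound found open at the confirmation visit resumes the weekly assessments (tracing, photograph, adverse event form) to Week 12 and may qualify again with a new confirmation visit.
2. In Section 3, state that Percent Wounds Closed counts only confirmed closures.
3. In Section 3, date time to closure from the first visit of the closure that was confirmed.
4. Reconcile Section 1 (the assessment and endpoint rows), Sections 3, 5.4 and 5.6, and Appendix A with these rules.

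The change should be worded as resumption after a failed confirmation. Continuing weekly assessment until closure is confirmed would be different: it could add a visit between first closure and confirmation for every patient who closes.

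Treatment of a reopened wound is for the sponsor to state separately.

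The cost is protocol wording, a few extra weekly assessments for perhaps 1 to 3 patients under the assumptions above, and possibly a confirmation visit after Week 12 for a wound that re-closes late.

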### **Secondary Outcome Measures:**

- Decrease in Wound Area From Baseline [ Time Frame: Baseline and weekly for up to 12 weeks ]  
Wound area measurements will be made via tracing acetate every week for 12 weeks or until the wound is completely closed, whichever occurs first. Wound area will be verified via confirmatory visit within 2 weeks after complete closure has been first determined.
- Time to Wound Closure [ Time Frame: Baseline through 12 weeks ]  
The number of weeks until complete closure is first identified will be determined for each patient who has been deemed completely closed within the 12 week treatment period.

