## **5.6. Early Withdrawal**

Patients who withdraw prior to the 12 week endpoint who have not yet been confirmed to have completely closed at the confirmation visit will be contacted by phone and/or mail. The purpose of making contact will be to determine the status of the wound to the best of the patient's ability (i.e., healed, not healed, seeking additional treatment, not seeking additional treatment) and to complete as many of the patient-reported outcomes questionnaires as possible. Information obtained on these withdrawn patients will be counted toward the actual follow-up rate, but used only for the analysis of tertiary endpoints.

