### ADVERSE EVENT SEVERITY

Mild	AE is noticeable to the patient but does not interfere with routine activity and does not require medical treatment.
Moderate	AE interferes with routine activity but responds to symptomatic therapy or rest. Usually requires medical treatment.
Severe	AE that results in loss of life or limb.

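### Time to Wound Closure is defined only for wounds that close by Week 12, with no time-to-event method, so as written the summary is conditional on healing and omits the open time of all other wounds

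*Combined protocol and SAP*

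**What the plan says.** The documents bear on this outcome in five places.

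- **Definition (section 3, Secondary Outcome Measures).** The number of weeks to first identified closure "will be determined for each patient who has been deemed completely closed within the 12 week treatment period". Nothing is said about a value, or a censoring time, for any other patient.
- **Analysis (section 8.1).** "Descriptive statistics will be used to compare amongst experimental groups, along with confidence intervals where appropriate to measure effect size". The section adds that "statistics on the wound measurements over time and at the 12 week endpoint will be used to inform future study hypotheses". It names no Kaplan-Meier estimate, life table, censoring rule or rule for competing events, and no other section does.
- **Data available.** Section 3, Primary Outcome Measures: "Wound healing will be assessed every week for 12 weeks or until the wound is completely closed, whichever occurs first". Section 5.4 lists "Documentation of wound closure (if present)" among the weekly items. The time each wound is seen to remain open is therefore recorded for every patient who attends.
- **Withdrawals (section 5.6).** Patients who leave before confirmed closure are contacted by phone or mail. "Information obtained on these withdrawn patients will be counted toward the actual follow-up rate, but used only for the analysis of tertiary endpoints".
- **Use of the results (section 3).** The aim is to inform the design of a randomized controlled trial. There is no control group; the plan is to "Utilize historical / published data on outcomes using standard of care".

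**The concern.** A time defined only for wounds that close describes how fast the closers closed. It does not describe how long a treated wound stays open. A wound open for all 12 weeks contributes nothing, although it was examined every week. Two products with very different closure rates can then show nearly the same healing time.

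This matters because of the study's aim. Healing time is a natural input to a trial's event-rate and follow-up assumptions, and a closers-only figure used alone would make healing look faster than it is. The same care applies to the historical comparison: a closers-only time is not comparable with any published time that includes unhealed wounds. The documents do not say how the published sources define healing time.

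**Working it through.** The plan gives no closure rate, dropout rate or sample-size derivation, so there is no figure of its own to reproduce. What follows illustrates size under stated assumptions.

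**Inputs.** From the documents: 30 patients (sections 1 and 3), weekly assessment, 12 weeks. Assumed: 12-week closure P of 30%, 50% or 70%, constant weekly closure probability, no dropout.

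**Formulas.**
- Weekly closure probability h = 1 − (1 − P)^(1/12), which is 0.0293, 0.0561 and 0.0955.
- Probability of closing at week k: p_k = h(1 − h)^(k−1), k = 1 to 12.
- Mean restricted to 12 weeks = Σ k·p_k + 12(1 − P), which equals P/h.
- Closers-only mean = Σ k·p_k / P.
- All-patient median = first week at which the proportion still open is at most 0.5.

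At P = 50%: restricted mean = 0.5/0.0561 = 8.91 weeks; closers-only mean = (8.91 − 12 × 0.5)/0.5 = 5.82 weeks.

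| | P = 30% | P = 50% | P = 70% |
|---|---|---|---|
| Patients left out, of 30 | 21 | 15 | 9 |
| Patient-weeks observed (30 × restricted mean) | 307 | 267 | 220 |
| Patient-weeks left out (30 × 12 × (1 − P)) | 252 (82%) | 180 (67%) | 108 (49%) |
| Closers-only mean, weeks | 6.15 | 5.82 | 5.33 |
| Restricted mean, weeks | 10.24 | 8.91 | 7.33 |
| All-patient median, weeks | not reached | 12 | 7 |

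From 30% to 70% closure the closers-only mean moves 6.15 − 5.33 = 0.82 week, less than its own simulated sampling SD of 1.2 weeks at 30%. The restricted mean moves 10.24 − 7.33 = 2.91 weeks, against an SD of 0.6 to 0.8. The median of 12 at P = 50% is a boundary value: just below 50% closure it is not reached.

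**Other closure patterns.**
- *A subgroup that never heals*, with 95% of healers closed by Week 12: the closers-only mean is 3.9 weeks at all three rates, while the restricted mean is P × 3.895 + 12(1 − P) = 9.57, 7.95 and 6.33 weeks.
- *Closure that speeds up* (Weibull shape 2): closers-only mean 8.20, 7.93 and 7.52 weeks; restricted mean 10.86, 9.97 and 8.87; median not reached, 12 and 10.

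**Withdrawals.** With 20% dropout unrelated to healing, the closers-only means fall only to 5.9, 5.6 and 5.1 weeks. Closers observed, as a share of all enrolled, are about 27%, 46% and 65%, while Kaplan-Meier recovers 30%, 50% and 70%. If instead a 20% withdrawal came only from wounds that would stay open, Kaplan-Meier would read about 34%, 56 to 58% and 81 to 83%. The ranges reflect whether patients leave after or before a week's visit.

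**Events that preclude closure.** With such events in an assumed 5% of patients, censoring them would overstate 12-week closure by 0.6 to 1.6 percentage points, depending on P and on the same timing convention.

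**The case against.** The strongest reply is that the primary outcome already covers most of the gap. Percent Wounds Closed has a weekly time frame. With no dropout, the cumulative number closed by week k divided by 30 is exactly one minus the Kaplan-Meier estimate, so the weekly proportions, median and restricted mean can all be read from it. This stands, with two limits. Section 3 does not expressly promise a table for each week, and with dropout the two curves part. The omitted patient-weeks are missing from one secondary item, not from the study.

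It is also fair to say that the section 3 sentence is an outcome definition, that section 8.1 does not forbid a Kaplan-Meier display, and that a closers-only time is a legitimate conditional summary. All true. But the outcome is named without that condition, and the only wording on who receives a value points to closers alone.

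Finally, this is a single-arm case series with no hypothesis test or success criterion, and harm requires someone to use the closers-only figure by itself. That limits the weight of the point; it does not remove it, because informing a later trial is the stated aim.

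Two stronger readings are not supported. A reader might infer that the plan has an explicit rule excluding non-closers from analysis. It does not: their omission follows from the definition together with the silence of section 8.1. A reader might also infer that section 5.6 discards withdrawn patients' clinic visits. Its restriction follows directly on the phone and mail contact and most naturally covers only that information.

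**Conclusion.** The point holds as a should-fix matter on one descriptive secondary outcome. As written, Time to Wound Closure is conditional on healing and says little about how many wounds heal: 0.8 week of movement in the closers-only mean, against 2.9 weeks in the restricted mean, as closure goes from 30% to 70%. Those sizes rest on assumed closure rates, a constant weekly closure probability and no dropout. The two other patterns change the numbers but not the conclusion.

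The documents do not support reading this as bias in the primary result, which is unaffected. Nor do they show that the historical comparison is invalid, since the definitions used in the published sources are not given.

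**What to change.** In sections 3 and 8.1:

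1. Define time to first identified closure for all enrolled patients.
2. Censor patients without closure at their last clinic wound assessment or Week 12, whichever is first, with one exception: patients with an event that precludes closure (death, loss of the limb) stay in the risk set as not closed through Week 12. The protocol's own severity scale foresees such events ("AE that results in loss of life or limb").
3. Report the Kaplan-Meier curve with numbers at risk, weekly closure proportions, and the median with 95% CI, or a statement that it was not reached.
4. Label any closers-only time as conditional on closure.
5. State that censoring withdrawals assumes withdrawal is unrelated to healing, and show as a bound the curve with withdrawals kept as not closed.

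Optional: a sensitivity analysis counting only closures upheld at the confirmation visit, and a sentence in section 5.6 limiting its restriction to phone or mail information.

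**Cost.** A short amendment, which under section 10.1 needs sponsor and IRB/IEC approval, and standard analysis code. There are no new visits or data. The healing time will look less favourable, and the median may not be reached. Taking that as fewer than 15 of 30 closed, the binomial probability is 98.3%, 42.8% and 0.6% at 30%, 50% and 70% closure.
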